- Percentage of patients with sustained improvement (AChR-Ab-positive or MuSK-Ab-positive patient population) during the first treatment period and observation period (baseline to Day 64): a reduction of ≥ 3 points from the baseline of Myasthenia Gravis Activities of Daily Living Scale (MG-ADL) score that persists for at least 4 weeks

Secondary study endpoints:**Clinical response assessment:**

- Percentage of patients with sustained improvement (i.e. Entire Population) during the first treatment period and observation period (Baseline to Day 64): a reduction of ≥ 3 -point from the baseline of Myasthenia Gravis Activities of Daily Living Scale (MG-ADL) score that persists for at least 4 weeks
- Percentage of patients with sustained improvement (AChR-Ab-positive or MuSK-Ab-positive patient population) during the first treatment period and observation period (baseline to Day 64): a reduction of ≥ 3 points from the baseline of Quantitative Myasthenia Gravis (QMG) score that persists for at least 4 weeks

- Percentage of the time that patients remain in clinical improvement: Percentage of the time that patients achieve clinical improvement (≥ 3 Point Reduction from Baseline for MG-ADL Score) from Baseline to Week 24 (AChR-Ab-positive or MuSK-Ab-positive Patient Population)
- Percentage of patients with minimal clinical manifestations (Minimal Symptom Manifestation, MSE) at any visit during the first treatment period and observation period (baseline to Day 64) (AChR-Ab positive or MuSK-Ab positive patient population): MG-ADL score of 0 or 1
- Percentage of patients with early improvement during the first cycle of treatment (AChR-Ab positive or MuSK-Ab positive patient population): a reduction of ≥ 3 -point of MG-ADL score at any visit from baseline to Day 15
- Percentage of patients with sustained improvement (AChR-Ab-positive or MuSK-Ab-positive patient populations) during the second treatment period and observation period: a reduction of ≥ 3 points from the baseline of MG-ADL score that persisted for at least 4 weeks

Safety Assessments:

- Overall safety profile (adverse events, laboratory tests, vital signs, etc.) of HBM9161
- Change from baseline in albumin and LDL-C levels during the study

Pharmacodynamic Assessments:

- Change of baseline in serum total IgG, serum acetylcholine receptor antibody (AChR-Ab), and muscle specific tyrosine kinase antibody (MuSK-Ab), and change in serum complement (CH50, C3)

Immunogenicity Assessment:

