This phase is a randomized, double-blind, placebo-controlled, parallel-group, group sequential design. Trial procedures include screening period (2 weeks), first treatment period (6 weeks), observation period (4 weeks), individualized follow-up period (until the patient meets the criteria for re-treatment), second treatment period (6 weeks), observation period (4 weeks) and follow-up period (to 5 weeks after last dose of study drug or to Week 24, which occurs later); the total length of the double-blind period will be at least 24 weeks up to 28 weeks. The latest start of

retreatment in this study phase will be Day 127 (Week 18). Subjects will be dosed for up to two treatment cycles throughout the study. Subjects who complete this study will have access to enter an open-label extension trial (separate protocol) to receive open-label HBM9161 Treatment.

[figure not shown]
A total of 120 subjects with positive AChR-Ab or MuSK-Ab and up to 24 subjects with negative AChR-Ab and MuSK-Ab are planned for this phase (The randomization will end after approximately 120 subjects with positive serum AchR-Ab or MUSK-Ab are enrolled) and randomized into 2 treatment regimens in a 1:1 ratio. Arm 1 will receive HBM9161 680 mg; Arm 2 will receive placebo. Whether or not AChR-Ab or MuSK-Ab is positive, and whether or not concomitant steroids are used will be randomization stratification factors.

First, eligible subjects will be screened into the double-blind treatment phase and blindly assigned to receive either HBM9161 680 mg or placebo for the first treatment period, administered once weekly (QW) for 6 doses, followed by an observational follow-up of at least 4 weeks for the primary endpoint analysis on Day 64.

Subjects who complete the first treatment period will start the administration of the second treatment period if they meet the dosing criteria for the second treatment period at Week 9. Otherwise they will be followed individually until they require a second cycle of therapy or until Week 24.

The second treatment period will be administered once weekly (QW) for a total of 6 doses in the first treatment period, followed by an observation period (4 weeks) and a follow-up period (5 weeks after the last dose of study drug or until Week 24 (which occurs later). Subjects will be dosed for up to two treatment cycles during the study, with the start of the second treatment period no later than Day 127 (i.e. Week 18).

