 - Double contraception: condom or cervical cap (diaphragm or cervical cap) plus spermicide (foam/gel/cream/suppository); or
 - An intrauterine device, implanted by a qualified physician; or

- Estrogen vaginal ring; or
- Contraceptive patch.

4. Male subjects must use effective contraceptive methods or have their heterosexual partners use effective contraceptive methods during their participation in this clinical trial.

5. Meets MGFA myasthenia gravis clinical classification IIa-IVa (includes types IIa, IIb, IIIa, IIIb, and IVa) at the screening visit and at the baseline visit.

6. Positive or negative AchR-Ab/MUSK-Ab at the screening visit and meets at least 1 of the following 3 criteria:

- a. Repeated electrical stimulation indicates neuromuscular junction transmission disorder (including medical history record);
- b. Positive Tensilon test or neostigmine test (including medical history record);
- c. The patient's MG symptoms improve after treatment with oral cholinesterase inhibitors at the judge of the physician.

7. MG-ADL score ≥ 5 and eye muscle-related score less than 50% of the total score at screening visit and baseline visit.

8. QMG score ≥ 11 at screening visit and baseline visit.

9. Subjects with stable treatment for myasthenia gravis at the randomization visit (Visit 2), where stable treatment is defined as follows (at least one is used):

- a. Cholinesterase inhibitors: stable dose for more than 4 weeks at randomization visit; and suspended for more than 12 hours when all clinical assessments are conducted;
- b. Corticosteroids: start at least 3 months prior to randomization visit and stable for at least 1 month at randomization visit (The total daily dose of glucocorticoids should not exceed prednisone 40 mg or equivalent) ;
- c. Immunosuppressants:
 - Azathioprine: start at least 12 months prior to the randomization visit and stable for at least 4 months at the randomization visit.
 - Other immunosuppressive drugs (e.g., cyclophosphamide, cyclosporine A, tacrolimus, mofetil, methotrexate, etc.): start at least 6 months prior to the randomization visit and at a stable dose for at least 3 months at the randomization visit.

10. If taking a statin, a medical history is required to document that the dose and regimen have been stable for 2 months prior to the Screening Visit.

11. Subject is willing and able to modify current disease therapy per protocol requirements at the discretion of the investigator.

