This stage is a group sequential statistical design, and the statistical hypothesis test will be performed at 1-sided of overall 0.025 significant level for efficacy endpoints. Trial sample size is based on the primary efficacy endpoint (i.e. sustained MG-ADL response rate within 9 weeks) in the population of AChR-Ab positive or MuSK-Ab positive patients, and the target power of the trial is 90%. An interim analysis will be performed when the first 67% (approximately 80 cases) of autoantibody-positive patients complete primary endpoint assessment. The overall class I error of statistical hypothesis testing is controlled by the Hwang-Shih-DeCani α -spending function; if statistical significance is reached at the significance level at 1-sided of 0.0063 in interim primary analysis, it can be considered that the trial is terminated prematurely (the follow-up of enrolled subjects is continued), otherwise the trial is continued, and 1-sided of 0.0230 level of significance will be applied in the final analysis. If the test for the primary endpoint is statistically significant, the sequential testing of full population will be treated at the same significance level (i.e., including both antibody-positive and antibody-negative populations). If the statistical test of full population is also statistically significant, the sequential testing will be performed at the significance level of 1-sided of 0.0159 (i.e., P Ocock Border) for remaining secondary efficacy endpoints.

The statistical hypothesis of dichotomous data will be statistically tested with normal distribution approximation, and the same normal distribution approximation will also be used for the calculation of 95% confidence interval. Missing assessments in the primary analysis will be imputed as not meeting the response threshold, and efficacy responses achieved after rescue treatment use will be treated as not meeting the efficacy response condition in the statistical analysis.

Descriptive statistics will be used for continuous data, and further analysis will be performed according to appropriate statistical analysis method (such as Kaplan-Meier, etc.).

An external independent data monitoring committee (iDMC) will be responsible for the conduct of the interim analysis and data review, and the independent data monitoring committee charter and interim statistical analysis plan (including iDMC recommended guidelines) will be finalized prior to enrollment of the first subject in Phase 3.

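### The Phase 3 primary test names no covariate; adjusting for baseline MG-ADL could add roughly 0 to 5 points of power with no extra patients, provided the interim test is safeguarded

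*Protocol*

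**What the plan says.** The Phase 3 primary endpoint, in antibody-positive patients, is "a reduction of ≥ 3 points from the baseline of Myasthenia Gravis Activities of Daily Living Scale (MG-ADL) score", lasting at least 4 weeks between baseline and Day 64. Phase 3 inclusion criterion 7 requires "MG-ADL score ≥ 5 and eye muscle-related score less than 50% of the total score at screening visit and baseline visit"; it sets no upper limit.

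The Phase 3 study design plans 120 antibody-positive subjects, "randomized into 2 treatment regimens in a 1:1 ratio". The stratification factors are antibody status and concomitant steroid use. Baseline MG-ADL is not one of them.

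Under Phase 3 Statistical Methods, "The statistical hypothesis of dichotomous data will be statistically tested with normal distribution approximation", and the 95% confidence interval uses the same approximation. The section also fixes the treatment of missing and post-rescue assessments (non-response), the 90% target power, the interim at about 80 antibody-positive patients, and the one-sided levels of 0.0063 (interim) and 0.0230 (final). It names no covariate or stratum for the test.

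**The concern.** A fixed 3-point fall demands different things of different patients. Someone entering at 5 must reach 2 or less, a 60% fall (3/5). Someone entering at 15 must reach 12, a 20% fall (3/15). The endpoint's construction therefore makes a link between baseline score and response plausible in both arms.

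The score is known for everyone, because eligibility and the endpoint both need it. If it predicts response, a test without it carries avoidable variance, and a chance difference between arms in baseline severity stays in the estimate. With about 60 patients per arm and no stratification on the score, such a difference can be large enough to affect a single trial's result.

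**Working it through.** **Inputs from the Protocol.** 120 antibody-positive subjects, 1:1, so 60 per arm; one-sided 0.025 overall; 90% target power; interim at 67% (about 80 patients, 40 per arm); nominal levels 0.0063 and 0.0230.

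**Assumed, because the text gives no figures.** The control response rate, the baseline MG-ADL distribution (range 5 to 20, mean 8.3, SD 3.0), and the odds ratio (OR) of response per SD of baseline (1.0 to 3.0).

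**1. The plan's own figures.** Hwang-Shih-DeCani spending with γ = −4 (assumed) at information 0.67 gives 0.0063 and 0.0230, with overall alpha 0.0250, so the stated levels reproduce. The 90% power cannot be reproduced without response rates, but it can be checked for coherence with

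n per arm = [z_α√(2p̄q̄) + z_β√(p₀q₀ + p₁q₁)]² / (p₁ − p₀)².

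For 30% v 58.9%: [1.960 × 0.703 + 1.282 × 0.672]² / 0.289² = 2.239² / 0.0835 ≈ 60. Control rates of 10% to 50% give detectable differences of about 24 to 29 points. Power with the two stated boundaries is then 0.896.

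**2. What adjustment buys.** Two tests were compared at a single look (60 per arm, one-sided 0.025, 20,000 trials per cell):

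- unadjusted: z = (p̂₁ − p̂₀) / √(2p̄q̄/n);
- adjusted: Δ = mean over all patients of [p̂(treated, xᵢ) − p̂(placebo, xᵢ)] from a logistic model with treatment and baseline score, divided by an influence-function standard error.

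The rate pairs were 20% v 48%, 30% v 59% and 40% v 69%; unadjusted power was 0.90 to 0.92.

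| OR per SD | Variance ratio, unadjusted/adjusted | Change in power (points) |
|---|---|---|
| 1.0 | 0.99 | −0.2 to +0.1 |
| 1.3 | 1.01 | 0 to +0.5 |
| 1.5 | 1.03 | +0.7 to +1.1 |
| 2.0 | 1.08 to 1.10 | +1.7 to +2.7 |
| 3.0 | 1.19 to 1.22 | +4.1 to +4.9 |

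Simulation error on power is about 0.2 points (√(0.9 × 0.1/20,000) = 0.002). In patient terms, a ratio of 1.08 to 1.10 is worth 120 × 0.08 to 120 × 0.10, or about 10 to 12 subjects; at 1.03 it is about 4.

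A different assumed baseline (range 5 to 16, peak about 8.5) with ORs per point of 1.11, 1.22, 1.35 and 1.49 gave 89.9 to 90.2%, 89.7 to 90.9%, 89.8 to 92.3% and 89.3 to 93.8%, which is the same picture.

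**3. Chance imbalance (30% v 58.5%).** The 97.5th percentile of the baseline difference is 1.96 × √(2/60) = 0.36 SD. At OR 2, the mean of p(1 − p) is about 0.226 × (1 − 0.10) = 0.204, taking 0.10 as the share of variance explained. The shift in the crude difference is 0.36 × ln 2 × 0.204 ≈ 0.05, or 5 points. In the tenth of simulated trials with the least favourable imbalance, unadjusted power was 83%, 77% and 69% at OR 1.5, 2 and 3; adjusted power was 90%, 91% and 95%.

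**4. Type I error.** At 60 per arm and nominal 0.025, rejection was 0.026 to 0.029 adjusted and 0.025 to 0.030 unadjusted, so there is no material difference. At the interim (40 per arm, nominal 0.0063):

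| Test | Null rejection rate |
|---|---|
| Unadjusted pooled z | 0.006 to 0.007 |
| Adjusted Wald, uncorrected | 0.008 to 0.009 |
| Adjusted Wald, simple degrees-of-freedom correction | 0.007 to 0.008 |
| Score test for treatment, same logistic model | 0.006 to 0.007 |

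The score test estimates its variance under the null. It holds the unadjusted level and keeps most of the power gain.

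**The case against.** **The SAP may already do this.** The text does not call the test unadjusted, and a stratified or standardised difference would also rest on a normal approximation. Covariates are often left to the SAP, which is not at hand. This stands to the extent that one cannot conclude that the sponsor has rejected adjustment. But the section is not simply silent: it fixes the form of the test, the interval method, the missing-data rule and the levels. Read plainly, that is a two-sample comparison of proportions, and it is the natural place to name the covariates.

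**A reader might infer that the planned test is biased or invalid.** The Protocol does not support that. After 1:1 randomisation the unadjusted test keeps its error rate, because chance imbalance is already in its standard error.

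**A reader might infer that adjustment is sure to add power at no cost.** That is not supported either. The Protocol gives no association between baseline and response. Patients with high scores have more room to fall but could also be harder to treat. With no association the change is nil or a trivial loss. There are costs too: a plain logistic test would move the target to a conditional odds ratio unless the difference is standardised, and an uncorrected Wald test spends too much alpha at the interim. Both objections stand, and they shape the recommendation.

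**Conclusion.** The point holds as a recommended efficiency improvement. The stated primary test names no covariate, although the endpoint's construction makes an already collected baseline score a plausible predictor and randomisation does not balance it.

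The expected gain is about 0 points of power for a weak association (OR per SD up to 1.3), 1 to 3 for a moderate one (1.5 to 2) and 4 to 5 for a strong one (3). These figures rest on assumed response rates, an assumed baseline distribution and a single final look. The further benefit is protection of this one trial against an unlucky baseline split. The planned test remains valid and nothing in the Protocol is contradicted.

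**What to change.** Before any unblinded interim data exist, state in Phase 3 Statistical Methods, or in the SAP with a cross-reference, that:

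- the primary analysis is adjusted for baseline MG-ADL (continuous) and concomitant steroid use, a randomisation factor that the stated test also leaves out;
- the reported effect is the marginal risk difference, standardised from a logistic model;
- the 0.0063 and 0.0230 decisions use a score test from that model or a small-sample-corrected variance, with type I error at the interim size checked by simulation (a simple degrees-of-freedom correction did not fully restore the level above);
- the full-population test also adjusts for antibody status, and the QMG responder endpoint uses baseline QMG;
- the unadjusted difference is kept as a supportive analysis.

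Sample size, nominal levels, data collection and the marginal risk difference as target are unchanged. The cost is additional programming and the variance safeguard, with its simulation check, at the interim.

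### Does one 95% interval for all binary endpoints clash with Phase 3 tests run at stricter levels?

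*Protocol*

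**What the plan says.** All of this stands in the protocol, under Phase 3 Statistical Methods unless another heading is named.

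- Overall error: "the statistical hypothesis test will be performed at 1-sided of overall 0.025 significant level for efficacy endpoints".
- The interim look comes when the "first 67% (approximately 80 cases) of autoantibody-positive patients complete primary endpoint assessment". The trial may stop early "if statistical significance is reached at the significance level at 1-sided of 0.0063 in interim primary analysis". Otherwise "1-sided of 0.0230 level of significance will be applied in the final analysis".
- After a significant primary result, "the sequential testing of full population will be treated at the same significance level". If that test also succeeds, "the sequential testing will be performed at the significance level of 1-sided of 0.0159" for the remaining secondary endpoints.
- The next paragraph, on dichotomous data, sets the normal-approximation test and then says "the same normal distribution approximation will also be used for the calculation of 95% confidence interval".
- Phase 3 study design plans 120 antibody-positive patients at 1:1, and "up to 24 subjects with negative AChR-Ab and MuSK-Ab are planned for this phase".

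The text does not say whether the interval is for the treatment difference or for each arm's rate. It does not name the variance form, and it attaches no decision to the interval.

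**The concern.** A two-sided 95% interval corresponds to a one-sided 0.025 test, and no individual test in this plan uses that level. The interval and the test share one approximation but not one critical value, so they can disagree.

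Two cases would reach a report. A remaining secondary endpoint could have p between 0.0159 and 0.025. Or, after a stop at the interim, the full population could have p between 0.0063 and 0.025. In either case an endpoint that formally failed would appear beside an interval that excludes zero, and some readers would take it as positive. In a confirmatory trial with a strict testing order that is a fair worry about reporting.

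Two related doubts come up. Plain Wald limits cover slightly less than 95%, and a raw difference after optional early stopping is somewhat biased.

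**Working it through.** **1. The plan's own levels.** The protocol does not give the Hwang-Shih-DeCani parameter. Assuming −4 and t = 0.67, the interim spend is 0.025 × (1 − e^(4×0.67)) / (1 − e^4) = 0.00634. Solving the bivariate normal with correlation √0.67 gives 0.02302 for the final look, and the constant two-look Pocock level is 0.01594. These round to the stated 0.0063, 0.0230 and 0.0159, so the levels are sound.

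**2. Matching interval levels**, 100 × (1 − 2α), with width relative to a 95% interval:

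| One-sided α | Critical z | Matching interval | Width ratio |
|---|---|---|---|
| 0.0063 | 2.495 | 98.74% | 2.495/1.960 = 1.27 |
| 0.0230 | 1.995 | 95.40% | 1.995/1.960 = 1.02 |
| 0.0159 | 2.147 | 96.82% | 2.147/1.960 = 1.10 |

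At the final primary analysis the gap is negligible. If the primary misses 0.0063 at the interim, the trial simply continues. That leaves the two cases described above.

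**3. A secondary endpoint.** The counts are assumed: 30/60 v 19/60. The difference is 18.3 points.
- Pooled standard error 8.97 points: z = 18.33/8.97 = 2.043, p = 0.0205. This fails 0.0159. The unpooled p is 0.0188 and also fails.
- Unpooled standard error 8.82 points: the 95% interval is 18.33 ± 1.960 × 8.82 = 1.1 to 35.6, and the 96.82% interval is 18.33 ± 2.147 × 8.82 = −0.6 to 37.3.
- Score limits at 95% are 0.7 to 34.9 and still exclude zero, so changing the type of limit does not remove the disagreement.

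**4. The full population at an interim stop.** The counts are assumed, with 8 antibody-negative patients per arm. Positives 24/40 v 12/40 give p = 0.0035, which crosses 0.0063. Adding negatives 2/8 v 3/8 gives 26/48 v 15/48, a difference of 22.9 points with z = 2.270 and p = 0.0116, which fails 0.0063. The 95% interval is 3.7 to 42.2 and the 98.74% interval is −1.6 to 47.4.

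**5. How often.** The protocol gives no response rates, so ranges are shown. For one secondary, exact enumeration at 60 per arm with placebo rates of 15 to 40% gives these chances of disagreement:

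| Power | Pooled test, unpooled interval | Same variance form for both |
|---|---|---|
| 90% | 2.9–3.6% | 2.4–3.3% |
| 80% | 4.8–6.2% | 4.0–5.5% |
| 50% | 7.4–9.0% | 6.5–8.3% |

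The right-hand column is closer to the protocol, which uses the same approximation for test and interval. Neither column allows for the testing order.

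For the full population, given an interim crossing and 8 negatives per arm, disagreement occurs in 4–6% of cases if the negatives share the effect, 8–13% if they have half of it and 14–22% if they have none.

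**6. Would level-matched intervals help?** Take a later secondary blocked because the one before it failed, both with equal power (normal model, correlation 0 to 0.8). The blocked endpoint's own 96.82% interval still excludes zero in 7–16% of trials at 80% power and 4–9% at 90% power. It cannot be claimed, whichever interval is printed.

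**7. Coverage and bias.** Enumeration of 40 then 60 per arm, treating every crossing as a stop, gives mean coverage of 94.3% for Wald limits and 94.9% for score limits at a nominal 95%. The raw difference is biased by 1.2 to 1.4 points. The bias comes from optional stopping, not from the interval level.

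**The case for a change.** The strongest case for a change is that this is text the protocol states, not detail left to the SAP. It ties the interval to the test's own approximation, gives it another level, and does not call it nominal. The difference between arms is the natural reading. Four binary secondaries fall under 0.0159: sustained QMG improvement, minimal manifestations, early improvement and second-period improvement. Disagreement is therefore possible more than once, and one sentence added before unblinding would cost nothing.

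The arithmetic and the possibility of disagreement stand. The step from there to a defect does not. The protocol nowhere says that the interval inverts a test, and a two-sided 95% interval is what readers expect beside an overall one-sided 0.025. Whether to print it with a label or at another level is a reporting convention that protocols commonly leave to the SAP, which is not at hand here.

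The stronger remedies are weaker still. Level-matched intervals leave blocked endpoints as open to misreading as before. Score limits are themselves a normal approximation, so the protocol does not exclude them, and they do not remove the disagreement. A bias-adjusted estimate is a separate matter that the interval level does not touch. The interim case also needs a crossing, an actual stop (which the protocol makes optional) and a miss in the full population.

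**Conclusion.** The disagreement is real but has no consequence for the trial's conclusions. Run exactly as written, the plan makes the same success and failure calls, with the same type I error and power, whatever level the interval carries.

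The size is modest: about 2–4% of trials for one secondary at 90% power and 7–9% at 50% power. This assumes an interval for the treatment difference, 60 per arm and placebo rates of 15–40%, and it ignores the testing order. The interim full-population case is more frequent once a crossing is given, but it rests on an assumed 8 negatives per arm and on an optional stop.

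A conventional 95% interval beside stricter tests is a fair trade-off. It is familiar and comparable across trials, and it is narrower than the matched intervals. A note that the intervals are nominal and that success follows only from the hierarchical tests is something analysts add as routine. It does not need a change to the plan.
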